4.2 Inclusion Criteria

An individual must meet all the following inclusion criteria to be eligible to be included into the study:

1. Individual's provision of a signed and dated electronic informed consent document indicating that the subject has been informed of all pertinent aspects of the study before any assessment is performed.
2. Healthy Adults, 18-64 years of age at the time of electronic consent (does not exclude any ethnicities, races, or gender identities)
3. Individual is seeking to improve their energy/less fatigue levels
4. Individuals whose baseline score (assessed during pre-screening) is ≥ 10 on the dimension of general fatigue of the Multidimensional Fatigue Inventory (MFI) and a score ≥ 3 for at least ten of the 20 questions of the MFI
5. Individuals who are willing and able to comply with all study related activities as shown in the Schedule of Activities.
6. Individuals who reside in the United States (except for Hawaii and Alaska)
7. Individuals who own a mobile device, tablet or computer with access to stable internet connection and are willing to use their device to complete study surveys and assessments

4.3 Exclusion Criteria

An individual who meets any of the following criteria will be excluded from the study:

1. Individuals who are an employee of **CCI**, either directly involved in the conduct of the study or a member of their immediate family; or a Haleon employee directly involved in the conduct of the study or a member of their immediate family.
2. Individuals who have participated in other studies (including non-medicinal studies) involving investigational product(s) within 30 days prior to study entry and/or during study participation.

Property of Haleon- Confidential

May not be used, divulged, published or otherwise disclosed without the consent of Haleon

CCI Abbreviated Clinical Protocol Template v1.0

3. Individuals who are pregnant, lactating, or plan to be pregnant or lactating during the course of the study (self-report).
4. Individuals with known or suspected intolerance or hypersensitivity to any study materials (or closely related compounds) or any of their stated ingredients.
5. Individuals who are hypertensive or salt-sensitive should be excluded from this study.
6. Individuals who report being a heavy drinker (defined as drinking 3 or more alcoholic beverages per day).
7. Individuals who are unable to read and understand English.
8. Individuals who report current and/or recent (up to 3 months ago) major illnesses and/ or major surgery
9. Individuals who report a planned surgery during the study duration.
10. Individuals who report a diagnosis of heart failure, heart rhythm disturbances, severe liver disease, severe mental health diagnosis, or severe renal failure.
11. Individuals who report taking medications (in the previous 21 days) that have well established moderate or severe interaction with any of the study product ingredients: Anticoagulants, antihypertensives, anxiolytics, antidepressants, chemotherapy, immunotherapy, sedative hypnotics, medications that warn against grapefruit consumption, corticosteroids at doses greater than 5 mg per day, diabetic medications, oral anti-infectives (antibiotics, antifungals, antivirals) to treat an acute infection, antipsychotics, Monoamine Oxidase Inhibitors (MAOIs), or thyroid products.
12. Individuals who are currently taking a multivitamin or have taken a multivitamin in the past 30 days & are not willing to stop taking a multivitamin for the duration of the trial.
13. Individuals who are currently taking other Vitamin C or B supplements or have taken Vitamin C or B supplements in the past 30 days & are not willing to stop taking other Vitamin C or B supplements for the duration of the trial.
14. Individuals who are currently consuming energy drinks or energy shots or have consumed an energy drink or energy shot in the past 30 days & are not willing to stop consuming energy drinks and energy shots for the duration of the trial.
15. A subject who has previously been enrolled in this study.
16. A subject who, in the opinion of the investigator or delegate, should not participate in the study.

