5.3 Pre-screening Assessments

Prior to their scheduled Screening and Baseline virtual visit, subjects will be asked to complete the following:

- Medical & concomitant medication history
- Demographic information
- The MFI
 - Following MFI completion, the participant's MFI score will be automatically calculated via the Citrus platform to determine eligibility. A subject is considered eligible if their baseline score is ≥ 10 on the dimension of general fatigue of the MFI and a score ≥ 3 for at least ten of the 20 questions of the MFI.

Note: If the participant is not eligible based on responses to the above items, a member of the study team will notify and screen fail the participant.

Property of Haleon- Confidential

May not be used, divulged, published or otherwise disclosed without the consent of Haleon

CCI [REDACTED] Abbreviated Clinical Protocol Template v1.0

5.4 Screening & Baseline: Virtual Visit 1

During the Screening and Baseline virtual visit, a trained member of the study team will verify the subject's identification (i.e. driver's license or government issued passport) on camera at the beginning of the visit. Should the subject elect not to show a form of identification or is unable to provide a valid identification at the beginning of the virtual visit, the visit may be rescheduled, or the subject may be considered a screen failure.

Following subject identification verification, the following visit procedures will be performed:

- Review self-reported medical and concomitant medication history
- Review inclusion/exclusion criteria
- Complete supplemental QoL questionnaire
- Provide instructions for the completion of the study questionnaire, daily diaries, and storage, preparation and administration of the study product
- Verify address for study product shipment
- Answer any questions the subject may have about the study

If the responses to all screening criteria are fulfilled, the subject will be considered enrolled. At enrollment, the following activities will occur:

- The subject will move forward to randomization into one of two study groups (on a 1:1 allocation) as follows: Group 1) Emergen-C Core Super Orange Powder or Group 2) Placebo.
 - Upon group allocation, subjects will be shipped the study product. Neither the subject or study team will be made aware which group arm the subject is allocated to.

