7.3 Blinding and Randomization

Qualifying subjects will be centrally randomized into one of two study groups using a randomization list provided by Haleon Clinical Supplies. Before the study is initiated, training and directions for the randomization will be provided to the investigator study team. Study products will be dispensed in sequential order as per the randomization schedule. CCI [REDACTED] will submit a list of subject ID numbers and corresponding kit codes to the Vendor each day for study product shipment. Only subjects who meet the study inclusion criteria will be randomized to a study product.

This study is described as double-blind (i.e., the clinical examiner and study participants will be blinded to the study product each subject receives). Additionally, investigator staff involved in the clinical or safety assessments, study statistician(s), data management staff, other employees of the sponsor (including the sponsor's Clinical Research Scientist (CRS)) and vendors acting on behalf of the sponsor who may influence study outcomes, will also be blinded to treatment allocation.

To maintain the blind throughout the study:

- Subjects will see and use only one of the two study products during the study. They will be instructed not to discuss the appearance, usage, or perceived performance of their allocated study product with staff involved in clinical assessments or with other study subjects.
- The study product will be provided to the CCI [REDACTED] preferred vendor in unmarked cartons masking their identity and obscure any branding on the commercial product with a study label affixed. Both study products (treatment and placebo) are packaged in individual, unmarked, identical foil sachets.
- The study product will be supplied in individual packs (cartons); each large carton will contain three smaller cartons, each containing 30 sachets of study product (90 sachets total). Each subject will receive one large carton, marked with a kit number containing only their randomized study product; product codes will not be used.

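### No criterion stops two members of one household from enrolling, which leaves an avoidable and undetectable route to mixing sachets from both arms.

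*Protocol*

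**What the plan says.** **Eligibility (Protocol 4.2 and 4.3).** Three exclusions come close to the point. Exclusion 15 excludes "A subject who has previously been enrolled in this study", which is the same person. Exclusion 1 reaches family members, but only those of study personnel: on the sponsor's side, "a Haleon employee directly involved in the conduct of the study or a member of their immediate family". Exclusion 16 is a general discretion: "A subject who, in the opinion of the investigator or delegate, should not participate in the study". None mentions a household or an address.

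**Recruitment and supply (Protocol 3, 5.4 and 7.1).** Recruitment is by social media advertising, the trial is fully decentralized, and allocation is 1:1 by individual. At Visit 1, before randomization, staff are to "Verify address for study product shipment". No comparison with the addresses of subjects already enrolled is described. Unused product is not returned.

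**Blinding (Protocol 7.3).** The listed measures include "Subjects will see and use only one of the two study products during the study" and "Both study products (treatment and placebo) are packaged in individual, unmarked, identical foil sachets". On kit identity the text says "Each subject will receive one large carton, marked with a kit number containing only their randomized study product". On conversation it says "They will be instructed not to discuss the appearance, usage, or perceived performance of their allocated study product", and this covers talk with assessment staff and with other subjects.

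**Dose record (Protocol 5.6, SAP 5.3.1).** The daily eDiary is one self-reported question on whether product was consumed. SAP compliance is computed from it.

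The SAP does not mention households, shared addresses or clustering.

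**The concern.** Adults aged 18 to 64 who want more energy and answer a social media advertisement could include partners or housemates. If two of them enrol and are allocated to different arms, Emergen-C and placebo sit in one home for 12 weeks in sachets that carry no marking. The condition that each subject sees and uses one product then depends on the two people keeping their supplies apart. No eligibility or allocation rule secures it.

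Two things could follow. Sachets may be swapped or shared, which narrows the treatment contrast on all five MFI domains. The two subjects may also compare products, which matters because every primary endpoint is self-reported fatigue.

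Neither event would show in the data. A subject who takes a housemate's sachet would still answer yes in the eDiary, would count as compliant, and could stay in the per-protocol set.

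**Working it through.** **Inputs from the documents**
- 300 randomized 1:1, 150 per arm (Protocol 8.1).
- 120 evaluable per arm, effect 0.5 SD, two-sided two-sample t-test at 1%, stated power over 90% (Protocol 4.1).

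**Inputs assumed, because the documents give none**
- *h*, the share of subjects who live with one other subject: 2%, 5% or 10%.
- *q*, the share of discordant homes that mix their kits evenly: 25% or 100%.
- Even mixing means each person takes half of each product, and the effect is proportional to the doses received. The contrast in such a home is then zero.

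**Step 1. The plan's own figure.** Noncentrality = 0.5 × √(120/2) = 3.873, with 238 degrees of freedom and a critical value of 2.597. The exact noncentral t calculation gives power 89.8%. The normal approximation gives 90.3%. The stated figure is therefore reproduced to within rounding, and 89.8% is the baseline below.

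**Step 2. Chance that a pair is discordant.** With 150 per arm, the probability that two given subjects fall in different arms is 150/299 = 50.2%, taken as one half.

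**Step 3. Subjects in discordant homes.** 300 × *h* × 0.5 = 3, 7.5 and 15 subjects for *h* = 2%, 5% and 10%. That is 1.5, 3.75 and 7.5 homes.

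**Step 4. Diluted effect.** d = 0.5 × (1 − *q* × *h*/2), with power from the same exact t-test at 120 per arm.

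| *h* | d, *q* = 25% | power | d, *q* = 100% | power |
|---|---|---|---|---|
| 2% | 0.4988 | 89.6% | 0.495 | 89.1% |
| 5% | 0.4969 | 89.4% | 0.4875 | 88.0% |
| 10% | 0.4938 | 88.9% | 0.475 | 85.9% |

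The loss is 0.2 to 0.9 percentage points if a quarter of discordant homes mix, and 0.7 to 3.9 points if all do. The result depends on *q* as much as on *h*, and neither is known.

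**Step 5. Would a mix-up be seen?** The eDiary asks whether product was taken, not from which kit. The sachets carry no mark, and leftover product is not returned. Unless a subject volunteers it, nothing described would reveal a swap.

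**The case against.** The strongest reply is that this is neither an error nor a contradiction. A reader might infer that two kits in one home already breach the one-product condition in 7.3. The documents do not support that. Each carton holds only that subject's allocated product, the sachets look the same, and the condition fails only if someone takes another person's supply. This part of the reply stands.

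Four further points also stand, wholly or in part:

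- **Direction.** Mixing pulls the estimate toward no difference. It cannot by itself create a false claim of benefit.
- **Unblinding.** A reader might infer that tasting both drinks would reveal the allocation. That needs a perceptible difference, and neither document describes the placebo's taste, colour or composition. The route is possible but cannot be sized.
- **Telling kits apart.** A reader might infer that two opened kits are indistinguishable. The text puts a kit number on the large carton and is silent on the three inner cartons. Sachets kept in a numbered carton remain identifiable, and only loose ones do not.
- **Shared colds.** A reader might infer that housemates make the exploratory symptom-day analyses materially wrong. Only exploratory endpoints are involved. Under individual randomization, same-arm pairs raise the variance of the contrast and opposite-arm pairs lower it, so with about half of each the effects largely cancel.

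There are also partial safeguards: the carton kit number, the no-discussion instruction, the discretion in exclusion 16, training on storage and use at Visit 1, and blinded review of any deviation that comes to light. Both housemates must also meet the MFI thresholds and pass the medical exclusions, which makes the upper end of the assumed range less likely. None of this prevents co-enrolment. An address check could exist in operational material not provided, but the protocol does not require one.

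**Conclusion.** The gap is real, and its likely effect is small. No criterion prevents household co-enrolment, and about half of any such pairs would be split across arms. A resulting mix-up would go unrecorded. On the assumed range of 2% to 10% of subjects living with another subject, power stays between 88.9% and 89.6% if a quarter of discordant homes mix evenly, and between 85.9% and 89.1% if all do, against 89.8% without mixing. These figures rest on two assumed rates and on the effect being proportional to the doses taken. They do not include any effect of unblinding, which the documents give no basis to estimate. The case for change is that the condition in 7.3 can be protected at very little cost. It is an optional improvement, not a defect that threatens the primary analysis.

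**What to change.** Add one line to Protocol 4.3: *Another member of the individual's household is, or has been, enrolled in this study.* At the Visit 1 address verification (Protocol 5.4), compare the shipping address with those of subjects already enrolled. That step already comes before randomization, so no new procedure or visit is needed. Sample size and analysis do not change. The cost is one exclusion line, a duplicate-address check, and a few otherwise eligible volunteers turned away.

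SAP Appendix 2 reports a decision already made at blind data review, so the criterion may come too late for subjects already enrolled. For them, the sponsor can count shared shipping addresses, before unblinding if that is still possible, and report the number. That would replace the assumed rate of co-residence above with an observed one.

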4.4 Lifestyle Considerations

As a real-world evidence study, there will be no lifestyle considerations.

5 STUDY PROCEDURES

This section lists the procedures and assessments to be completed at each planned study time point. However, as per nature of Real World Evidence (RWE) studies, if a subject fails to complete their daily questionnaire at any time point post-baseline, subjects will be permitted to continue in the study. The timing of each procedure is listed in the Table 5-1 Schedule of Activities section.

Property of Haleon- Confidential

May not be used, divulged, published or otherwise disclosed without the consent of Haleon

CCI [REDACTED] Abbreviated Clinical Protocol Template v1.0

5.1 Schedule of Activities

The Schedule of Activities (Table 5-1) provides an overview of the subjects virtual visits, study procedures and assessments. The investigator may schedule additional (unplanned) virtual visits to conduct additional evaluations or assessments required to protect the well-being of the subject. A detailed schematic of the Schedule of Activities is located in section 9.9 Schedule of Activities Schematic.

Table 5-1 Schedule of Activities

Visit	Treatment Period					
	Pre-screening	Visit 1 Screening & Baseline	Treatment Initiation	Virtual Visit 2	Virtual Visit 3	Virtual Visit 4
Study Day	Day-7 to Day -2	Day -7 to Day -2	Day 1	Week 4 Day 28 (+5)	Week 8 Day 56 (+5)	Week 12 Day 84 (+5)
Medical/Medication History ^a	X					
Demographics ^a	X					
Informed Consent	X					
Subject ID Verification		X				
Inclusions/Exclusion Criteria ^c		X				
Eligibility Assessment		X				
MFI ^a	X			X	X	X
Supplementary QOL questionnaire ^a		X		X	X	X
Randomization		X				
Participant Training		X				
Study Product Shipped		X				
Concomitant Medication Check		X		X	X	X
Adverse Event (AE/ Serious Adverse Event)		X	X	X	X	X
Study Product Administration ^b			X (Daily through Week 12 visit)			
Participant Daily eDiary ^d			X (Daily through Week 12 visit)			
Subject Conclusion/Subject Exit from Study						X
Exit Survey ^a						X

Footnotes:

^aSubject-reported (self-reported) assessments.

Property of Haleon- Confidential

May not be used, divulged, published or otherwise disclosed without the consent of Haleon

CCI [REDACTED] Abbreviated Clinical Protocol Template v1.0

^bSubject will take the study product in the morning of each day

^cSubject will self-report pregnancy status during Visit 1

^dSubject-reported (self-reported) they took the investigational product on that day.

The virtual site may contact subjects prior to study visits, either as part of pre-screening activities or as a reminder of the approaching scheduled visit. Further details should be included in the electronic informed consent (eICF).

5.2 Pre-screening

The study team will identify and recruit potential subjects via social media platform advertising. Potential subjects will be directed to the study web page where they will complete an online pre-screening questionnaire assessing their eligibility to participate in the study. The information collected from the pre-screening questionnaire serves as the preliminary screening tool to isolate potentially eligible participants from ineligible subjects. Subjects who successfully pass the pre-screening questionnaire are deemed potentially eligible for participation and are directed to complete an online eICF. Potentially eligible subjects who execute the eICF will receive a copy of the signed eICF via email.

5.2.1 Inclusion/Exclusion Criteria

Inclusion and exclusion criteria as per Section 4.2 and 4.3 will be collected via pre-screening survey and confirmed during the Screening and Baseline virtual visit with a trained & delegated study team member.

5.2.2 Demographics

The following demographic information will be collected: year of birth and age, sex at birth, race, ethnicity, height, weight, and smoking (including vaping) status.

5.2.3 Informed Consent

The eICF is a tool that assists in the consenting process by using multimedia components delivered by an electronic system. The eICF process for this study will be performed on the subject's mobile device, tablet or computer following successful completion of the study pre-screening questionnaire. Informed consent must be obtained before any study-specific activity is performed. Once the eICF has been signed and dated by the subject, the subject will be provided with a copy via email. An additional copy of the signed eICF will be saved as a Portable Document Format (PDF) in the virtual site file.

If, during a subject's participation in the study, the eICF undergoes any changes, each ongoing subject should receive a copy of this new information and be re-consented into the study. Each subject should be provided with a copy of the signed and dated amended consent form.

5.2.4 Medical History and Prior Medication/Treatment

Relevant medical and/or surgical history (in the previous 12 months) will be self-reported, including allergies or drug sensitivity and prior medications/treatments, including prescription and non-prescription drugs, dietary supplements and herbal remedies, that began before

obtaining informed consent will be recorded as the Medical History/Current Medical Conditions.

Female subjects only:

- Female subjects who report being pregnant or confirm planning pregnancy during the study will be discontinued from participation in this study.
- Given the potential impact of pregnancy on study outcomes, female subjects of child-bearing potential will be reminded to inform the investigator site immediately if pregnancy is known or suspected.

Relevant medical and surgical history, including allergies or drug sensitivity can be documented by the investigator or designee in the medical history form.

Please refer to section 9 for further details on Adverse Event and Serious Adverse Event Monitoring and to section 8.3.6.2 for further details on concomitant medications.

The investigator and/or delegated study team member will review inclusion/exclusion criteria, medical history and prior medications to confirm subject eligibility to participate in the study.

5.2.5 Enrolled Subjects and Screen Failures

An enrolled subject is one who has agreed to participate in the clinical study following completion of the informed consent process and who has directly and successfully met eligibility criteria to proceed beyond the screening visit.

Screen failures are defined as subjects who consent to participate in the clinical study but are not subsequently randomized to a study group.

To ensure transparent reporting of screen failure subjects, a minimal set of screen failure information will include demography and screen failure details (e.g., withdrawal of consent, eligibility criteria, any protocol deviations and any adverse events).

Individuals who do not meet the criteria for participation in this study (screen failure) will not be re-screened.

